7.2.2 Sampling technique

The sample aims to cover all eligible patients presenting over a 24 month period across **a number of** NHS Trusts. Retrospective work the study team has carried out has shown that it is feasible to achieve the required sample size during this time period however if recruitment is poor then there is scope to expand to other sites or to extend the duration of the study period. The different trusts are located across the UK and should produce an unselected cohort in terms of gender, educational achievement and socioeconomic background.

7.3 Recruitment

7.3.1 Sample identification

Eligible participants will be identified from weekly multidisciplinary team meetings (MDTs). These are attended by the usual clinical neuro oncology care team for the patient who will also make up the study team, thus no one outside of the usual care team will have access to patient identifiable data. The patient lists for the MDTs will be examined and patients meeting the eligibility criteria for the study will be identified.

No public recruitment (i.e. posters/leaflets/website) will be performed. It is UK practice that all newly diagnosed GBM patients must be discussed at a relevant MDT meeting. Participants will be attending for their usual NHS neuro oncology clinic appointment when they are recruited. The follow up assessment will also be done during their routine NHS follow up appointments. The only potential extra appointment would be if the patient requires an additional MRI scan. In these cases the travel costs for the participant and carer will be covered within reason.

7.3.2 Consent

Eligible participants will be approached at or soon after their initial neuro oncology outpatient clinic appointment after it has been confirmed that they are eligible for the study (i.e. they are to undergo radiotherapy treatment for treatment of their GBM). Treatment decisions are made prior to enrolment

within the study and are not affected by the study. Capacity assessments will be undertaken during this clinic appointment by a member of the clinical or study team who has the appropriate training prior to enrolment within the study. Capacity will be reassessed at each subsequent follow up (4 week and 8 week post treatment appointments). If participants lose capacity the participant would be withdrawn from the study. Identifiable data or tissue already collected with consent would be retained and used in the study. No further data or tissue would be collected or any other research procedures carried out on or in relation to the participant. This is outlined in the patient information sheet.

Eligible participants will be given a patient information sheet and adequate time to read and discuss any queries with a member of the study team during their outpatient consultation. If they agree to participate in the study then they will complete a written consent form. This consent form will include permissions for the study team to access their clinical records and pathological samples as well as performing the extra MRI sequences. The consent form will be received by a member of the study team (usually the oncology consultant or nurse specialist) during the outpatient consultation.

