4.2 Outcome

The primary outcome is the proportion of patients with a 10 point change in the EORTC QLQ C30 quality of life questionnaire (with the BN-20 brain and ELD14 elderly patient subsets of questions added) from baseline to 8 weeks.

The impact of side effects from cranial radiotherapy will also be assessed by the secondary outcomes of

- MOCA cognitive screening questionnaire
- use of corticosteroids
- degree of grade 3-5 CTCAE toxicity
- overall and progression free survival

5 STUDY DESIGN and METHODS of DATA COLLECTION AND DATA ANALYSIS

The BRITER study is an observational cohort study. Eligible patients will be identified during the multidisciplinary team meeting by the participants' usual care team. They will have previously been informed of their diagnosis and then will meet a member of the oncology team to discuss treatment options. Once it has been decided with them by their usual care team that they are to have radiotherapy treatment, they will be given a PIS. After the patient has had sufficient time to read the PIS and have any questions answered by a member of the study team they will be asked to complete a consent form. They will also undergo the baseline clinical assessments prior to starting any

radiotherapy treatment. This will be done during the outpatient appointment with the neuro oncology team.

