7.2 Sampling

7.2.1 Size of sample

Sample size calculations have been performed assuming a clinically significant end point of a 10 point change (SD=22.1 taken from the EORTC website reference guide) in EORTC QLQ questionnaire score between baseline and 8 weeks. Estimated sample size for one-sample comparison of proportion to hypothesized value assuming a 2 sided alpha of 0.05 and power of 0.9 gives a sample of

73. However, allowing for 20% attrition in questionnaire completion, this results in a sample size of 91. With 73 patients at 8 weeks, we will have 90% power for 5% significance to detect 5% of patients achieving a 10 point change in QoL. However, this small a proportion will only allow us to fit one variable in the model. It has therefore been recommended by the statistical team to aim for a recruitment target of 100 patients in order to fit the 5 MRI variables to the model.

Patients who are enrolled within CTIMP studies will not be eligible to be recruited into the study as they would introduce too many unknown variables for adequate statistical analysis with a cohort of this size.

Previous work done by this study group has shown this is a feasible recruitment target over 2 years.

The study team will review recruitment at 9 months and if it has not reached 25% then they will explore ways to increase recruitment, including opening at other sites.

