8.6 Data protection and patient confidentiality

All investigators and study site staff will comply with the requirements of the Data Protection Act 1998 with regards to the collection, storage, processing and disclosure of personal information and will uphold the Act's core principles.

No patient identifiable data will be accessed by anyone outside of their usual direct care team. The study members are all part of the usual direct care team. Patient identifiable data will be accessed by the study team in order to identify eligible participants from the MDM list and if necessary access their postal addresses in order to send them the initial PIS and consent form. All paperwork from the study will be recorded using the participant study ID numbers. Data will be pseudo anonymised locally and survival data will be collected on participants at the end of the study period. The study database created at the end of the study period once survival data has been collected will be fully anonymised. No patient identifiable data will be recorded on the study database. Data protection and confidentiality will be respected at all times. Data will be handled as per data management above.

Prior to MRI scans being transferred electronically via the national IEP system, the scans will be allocated the participants study ID by the local study team. No patient identifiable data will therefore be transferred electronically.

The database will be kept on password protected NHS computers within a locked office. The paper copies of the CRFs will be kept within secure NHS offices by the members of the local study team. Any transfer of data will be done via secure NHS.net e-mail systems or an encrypted USB however no patient identifiable details will be transferred off site.

The data will be stored for 5 years after the end of the study date.

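### Withdrawing patients who lose capacity removes their week-8 outcome, and read literally their later survival data, and no analysis is planned to deal with the likely bias

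*Combined protocol and SAP*

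**What the plan says.** Section 7.3.2 (Consent) has capacity reassessed at the 4- and 8-week post-treatment visits. If it has gone, three provisions apply:

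- Withdrawal: "If participants lose capacity the participant would be withdrawn from the study".
- Earlier data: whatever was gathered under consent before that point stays in the dataset and is analysed.
- Later data: "No further data or tissue would be collected or any other research procedures carried out on or in relation to the participant". No exception is made for dates of death or progression, or for data already in clinical records.

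The outcomes affected are in section 4.2. "The primary outcome is the proportion of patients with a 10 point change in the EORTC QLQ C30 quality of life questionnaire", measured from baseline to 8 weeks. The secondary outcomes include "overall and progression free survival".

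Section 8.6 says that "survival data will be collected on participants at the end of the study period", without saying whether withdrawn participants are included.

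Section 5 plans multivariable logistic regression of the 10-point change on the MRI parameters. It gives no rule for missing outcomes or withdrawal, no censoring rule for survival and no sensitivity analysis. The only provision for losses is in section 7.2.1, which inflates the sample "allowing for 20% attrition in questionnaire completion".

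**The concern.** The study asks whether a vulnerable brain on pre-treatment MRI predicts harm after radiotherapy. Section 1 lists cognitive defects among the side effects of radiotherapy, and the MOCA is a secondary outcome. A patient who can no longer consent has therefore probably deteriorated in the way the study wants to predict, and that loss may be related to the MRI scores themselves. Section 3 hopes to identify just such vulnerable patients.

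Two things are at stake. First, the primary outcome is missing for a group probably richer in deterioration than those who stay, so the proportion deteriorating is probably understated. The regression on completers may also be biased, most plausibly towards weaker MRI associations. Second, if survival follow-up stops at withdrawal and these patients are censored there, the analysis assumes that their outlook matches that of patients who kept capacity. If it is worse, survival is overstated.

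**Working it through.** **1. The plan's own allowance (section 7.2.1).** 73 / (1 − 0.20) = 91.25, stated as 91 (92 if rounded up). With 100 recruited, 73 evaluable patients remain if total losses are at most 1 − 73/100 = 27%. If capacity losses took the total to 30%, 73 / 0.70 = 104.3, so 105 would be needed. This allowance concerns the number of questionnaires. It does nothing about who is missing.

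**2. Primary outcome.**

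- From the documents: 100 recruited and 20% attrition, so 80 completers; 5% with a 10-point change, the proportion named in section 7.2.1.
- Assumed: 10 of the 20 missing patients lost capacity, and 5 to 10 of those would have deteriorated. The other 10 behave like completers. The 10-point change is taken as a worsening, since the protocol does not state its direction.
- Events seen: 80 × 0.05 = 4.
- True proportion: (90 × 0.05 + 5) / 100 = 9.5%, up to (90 × 0.05 + 10) / 100 = 14.5%.
- With 20% among completers (16 events): (90 × 0.20 + 5) / 100 = 23%, up to (90 × 0.20 + 10) / 100 = 28%. The relative error is smaller.

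**3. Overall survival, if censored at withdrawal.**

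- From the documents: average survival of 3 to 6 months (sections 2 and 3), used as the median before any loss of capacity; capacity checked only at two visits.
- Assumed: exponential times; capacity lost at 0.05 to 0.08 per month; death hazard 2 to 4 times higher afterwards; visits at about 1.6 and 2.5 months, or 2.1 and 3.0 months. A patient is censored at the first visit at which capacity has gone, and deaths before that visit count.
- Method: simulate a large cohort and compare the true median with the Kaplan-Meier median under this censoring.

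| Scenario (visits at 2.1 and 3.0 months) | True median | Censored median | Overstatement |
|---|---|---|---|
| Smallest: pre-loss median 3, rate 0.05, hazard ×2 | 2.84 | 2.89 | 0.05 months (about 2%) |
| Largest: pre-loss median 6, rate 0.08, hazard ×4 | 4.54 | 5.10 | about 0.6 months (12–13%) |

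The other combinations lie between these. With the hazard unchanged the two medians agree.

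**4. A second model as a check.** Here 10% or 20% of patients are assigned to lose capacity at a visit, with a hazard 3 times higher afterwards and an underlying median of 6 months. Deaths before the visit reduce the share actually withdrawn to about 8% or 16%.

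- 10% assigned: true 5.52 against censored 6.01, a difference of 0.49 months, inside the range above.
- 20% assigned: true 5.08 against censored 5.99, a difference of 0.91 months (0.91 / 5.08 = 18%), outside it.

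The range in step 3 therefore belongs to its assumptions and is not an upper bound.

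**5. The two sections side by side.** Section 7.3.2 forbids new data on or about a withdrawn participant. Section 8.6 collects survival on participants at study end. Section 7.3.2 also says the consent form covers access to clinical records, but it does not say that this permission outlasts loss of capacity. The specific rule would normally govern, and section 7.3.2 says that it is in the patient information sheet.

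**The case against.** The withdrawal rule is a deliberate ethical choice, disclosed to patients and consistent with requiring capacity at entry. That stands, and nothing here argues for questionnaires or procedures after capacity is lost.

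A reader might infer that these patients vanish from every outcome. They do not: data already collected are kept and used. A patient withdrawn at week 8 retains baseline and week-4 data, and any week-8 questionnaire returned before the visit would arguably be kept as well. Loss of capacity after week 8 falls outside the rule's two checks.

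A reader might also take it as settled that survival is informatively censored. The documents state no censoring rule, and section 8.6 can be read as including withdrawn participants. Censoring is the natural result of section 7.3.2 read literally, not a stated method.

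A reader might expect a larger survival bias. Starting from an 8-month median and censoring at the instant of loss gives 0.6 to 1.3 months. The documents support neither input: they give 3 to 6 months, and capacity is checked only at visits.

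Nor do they support saying that MRI associations would be reversed. No calculation above includes an MRI variable. Weakening is the plausible direction, but it is not shown.

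Finally, incapacity may reflect tumour progression rather than radiotherapy. Counting it as an event in the primary outcome would change a patient-reported endpoint into a composite. That is a fair reason to confine it to a sensitivity analysis.

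**Conclusion.** The point holds within these limits. As written, the plan leaves patients found to lack capacity by week 8 without a primary outcome, and it contradicts itself on whether their survival is followed.

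For the primary outcome, the likely effect is to understate deterioration: 5% seen against 9.5% to 14.5% under the step 2 assumptions. The MRI associations may be biased, by an amount that cannot be calculated from the documents.

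For survival, if censored at withdrawal, the overstatement of the median is about 0.05 to 0.6 months (2% to 13%) under the step 3 assumptions. It is larger if more patients are withdrawn and nil if prognosis is unchanged. The direction is firm wherever prognosis worsens with loss of capacity. The size is not, because the documents give neither the rate of loss nor the hazard afterwards. Survival is a secondary outcome whose analysis against MRI is exploratory, so the primary outcome is the more important part.

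**What to change.** 1. **Analysis plan (section 5).** Record loss of capacity, with its date, as the reason for a missing week-8 outcome. Keep the questionnaire-only definition as primary. Pre-specify a sensitivity analysis of the primary logistic regression that counts withdrawal for loss of capacity by week 8 as deterioration. In the step 2 example with 10 such patients, this moves the data from 4 events in 80 to 14 events in 90. The cost is a little more analysis, and the result must be read knowing that incapacity may be due to tumour progression.

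2. **Survival follow-up (sections 7.3.2 and 8.6).** Reconcile the two sections so that they say the same thing about withdrawn participants. Subject to ethics approval, add to section 7.3.2, the information sheet and the consent form a permission, given while the patient has capacity, for dates of death and progression to be taken from clinical records if capacity is later lost. This involves no contact or procedure after that point. The cost is an amendment that would apply only to new participants. For those already enrolled, the report should state how survival was handled after withdrawal.

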8 ETHICAL AND REGULATORY CONSIDERATIONS

8.1 Assessment and management of risk

Risk of significant harm to the participant is unlikely within this study. Participants who require a further MRI scan may require the administration of gadolinium contrast. This is generally safe and well tolerated however the risk profile of this will be discussed with the patient prior to administration and local policies will be followed if the patient has a reaction to the contrast agent. MRI scans are in general well tolerated and do not involve ionising radiation therefore do not carry with them any increased malignancy risk.

Participants will be attending clinic for their routine follow up visits when they complete the assessments and therefore will not need any extra visits to hospital. During their clinic visit they may need to spend slightly more time than they would usually do in order to complete the questionnaires. In order to minimise this we have allowed for carers/family/a member of the study team to assist with the self-reported questionnaires or for the patient to take the questionnaire home with them to complete and post back to the study team.

The participant's GP will be informed of their involvement within the study. If there are concerns from the answers to the questionnaires that the participants may be at risk of harm to themselves or to others then this will be discussed with the participant's GP or other teams. The participants will be aware of this. In the unlikely event that any psychological distress is caused to the participants by completing the questionnaires, we would address this within the clinic visit and if necessary refer to their GP or local psychiatric services for further support.

8.2 Research Ethics Committee (REC) and other Regulatory review & reports

Before the start of the study, a favourable opinion will be sought from a REC for the study protocol, informed consent forms and other relevant documents

Substantial amendments that require review by NHS REC will not be implemented until that review is in place and other mechanisms are in place to implement at site. All correspondence with the REC will be retained. The Chief investigator will produce the annual reports as required and will notify the REC of the end of the study. An annual progress report (APR) will be submitted to the REC within 30 days of the anniversary date on which the favourable opinion was given, and annually until the study is declared ended. If the study is ended prematurely, the Chief Investigator will notify the REC, including the reasons for the premature termination. Within one year after the end of the study, the Chief Investigator will submit a final report with the results, including any publications/abstracts, to the REC.

Regulatory Review & Compliance

Before any site can enrol patients into the study, the Chief Investigator/Principal Investigator or designee will ensure that appropriate approvals from participating organisations are in place. Specific arrangements on how to gain approval from participating organisations are in place and comply with the relevant guidance.

For any amendment to the study, the Chief Investigator or designee, in agreement with the sponsor will submit information to the appropriate body in order for them to issue approval for the amendment. The Chief Investigator or designee will work with sites (R&D departments at NHS sites as well as the study delivery team) so they can put the necessary arrangements in place to implement the amendment to confirm their support for the study as amended.

Amendments

If the sponsor wishes to make a substantial amendment to the REC application or the supporting documents, the sponsor must submit a valid notice of amendment to the REC for consideration. The REC will provide a response regarding the amendment within 35 days of receipt of the notice. It is the sponsor's responsibility to decide whether an amendment is substantial or non-substantial for the purposes of submission to the REC.

8.3 Peer review

8.4 Patient & Public Involvement

The study protocol and patient information sheet have been reviewed by the JAFFA panel - a patient and public involvement (PPI) lay research panel based at Brighton and Sussex University Hospitals Trust. Their feedback was instrumental in restructuring the protocol and PIS to make the design of the study clearer to understand and confirm the importance of using quality of life as the primary outcome.

A lay summary of the study was circulated to The Brains Trust PPI panel during the design of the study who again aided in the structure of the study and gave their full support. It was also sent to The Brain Tumour Charity Research Involvement Network, a group of brain tumour patients and their carers. They sent detailed feedback and felt the study was well explained and clear to understand and some points they raised surrounding the sequence of consenting and enrolling in the study led to an adaptation of the study protocol. They did not feel undergoing an extra MRI scan would be onerous to the participants. They unanimously agreed that the objectives of the study were worth pursuing and that it was a valid study question.

8.5 Protocol compliance

Accidental protocol deviations can happen at any time. They must be adequately documented on the relevant forms and reported to the Chief Investigator and Sponsor immediately.

Deviations from the protocol which are found to frequently recur are not acceptable, will require immediate action and could potentially be classified as a serious breach.

8.6 Data protection and patient confidentiality

All investigators and study site staff will comply with the requirements of the Data Protection Act 1998 with regards to the collection, storage, processing and disclosure of personal information and will uphold the Act's core principles.

No patient identifiable data will be accessed by anyone outside of their usual direct care team. The study members are all part of the usual direct care team. Patient identifiable data will be accessed by the study team in order to identify eligible participants from the MDM list and if necessary access their postal addresses in order to send them the initial PIS and consent form. All paperwork from the study will be recorded using the participant study ID numbers. Data will be pseudo anonymised locally and survival data will be collected on participants at the end of the study period. The study database created at the end of the study period once survival data has been collected will be fully anonymised. No patient identifiable data will be recorded on the study database. Data protection and confidentiality will be respected at all times. Data will be handled as per data management above.

Prior to MRI scans being transferred electronically via the national IEP system, the scans will be allocated the participants study ID by the local study team. No patient identifiable data will therefore be transferred electronically.

The database will be kept on password protected NHS computers within a locked office. The paper copies of the CRFs will be kept within secure NHS offices by the members of the local study team. Any transfer of data will be done via secure NHS.net e-mail systems or an encrypted USB however no patient identifiable details will be transferred off site.

The data will be stored for 5 years after the end of the study date.

